### 11.1 Adverse Events

Adverse events will be coded using the Medical Dictionary for Regulatory Activities (MedDRA)

Adverse events and SAEs will be recorded from the time the informed consent is signed through 30 days after the last dose of investigational product regardless of relationship to investigational product. This includes events occurring during the screening period, regardless of whether or not investigational product has been administered. Following the 30-day capture period for all AEs and SAEs, only those AEs/SAEs deemed related to investigational product or other protocol mandated procedures will be collected during the long-term follow-up phase of the study. If the subject undergoes retreatment with investigational product for a new AMR episode, AEs and SAEs will be captured as described above for the treatment of the initial occurrence of AMR. In addition, the following events of special interest, both serious and non-serious, will be closely monitored and reported to Shire GDS via SAE form throughout the study, regardless of relationship to investigational product: any thrombotic or thromboembolic event, any hypersensitivity reaction, any new episode of kidney allograft rejection (excluding AMR), and any kidney allograft failure.

An adverse event that increases in severity will be captured as a new event. Worsening of pre-treatment events, after initiation of investigational product, will be recorded as new AE. An AE (classified by preferred term) that occurs during the study will be considered a treatment-emergent AE (TEAE) if:

- it has a start date and time on or after the first dose of investigational product, or
- it has a start date and time before the date and time of the first dose of investigational product, but increases in severity on or after the date and time of the first dose of investigational product.

If more than 1 AE with the same preferred term is reported before the date and time of the first dose of investigational product, then the AE with the greatest severity will be used as the benchmark for comparison to the AEs occurring during the study under the preferred term. An AE that occurs more than 30 days after the date of the last dose of investigational product in a treatment period will not be counted as a TEAE. For example, an AE occurs more than 30 days after the last dose in the initial treatment period, but before the first dose of any new acute AMR treatment period will not be counted as a TEAE.

An overall summary of all AEs/TEAEs in each treatment group and/or treatment period will be presented respectively, including the number and percentage of subjects experiencing event, and absolute count of events with:

- Any AE/TEAE
- Any serious AE/ TEAE
- Any AE/TEAE related to investigational product in the opinion of the investigator
- Any AE/ TEAE leading to study drug discontinuation from the study
- Any severe AE/TEAE.
- Any AE/TEAE leading to death

The number and percentage of subjects and absolute count of events with AEs/TEAEs in each treatment group and/or treatment period will be tabulated respectively in the following ways:

- By SOC, preferred term
- By Maximum severity, SOC, and preferred term
- By SOC, preferred term for serious AE/TEAE
- By SOC and preferred term for AE/TEAE related to investigational product in the opinion of the investigator
- By SOC and preferred term for AE/TEAE leading to Death
- By SOC and preferred term for AE/TEAE leading to Study Drug Withdrawal

Total number of subjects on treatment for each treatment group will be given in all table headers.

For Serious AEs and AEs related to the investigational product, the table by SOC and preferred term will only be produced if there are greater than 5 events total. If there are less than or equal to 5 events, then only the listing will be provided.

All information about AEs collected on the CRF will be listed alongside the treatment, preferred term, and SOC.

## 11.2 Clinical Laboratory Variables

Descriptive statistics for clinical laboratory values (in SI units) and changes from baseline at each assessment time point will be presented by treatment group for the following clinical laboratory variables. Baseline is defined as the last measurement prior to the first dose of investigational product during the study .

**Chemistry**      albumin, alanine aminotransferase, alkaline phosphatase, aspartate aminotransferase, blood urea nitrogen (BUN), calcium, spot urine protein, carbon dioxide, chloride, creatinine, calculated eGFR, direct bilirubin, gamma-glutamyl transferase, glucose, lactate dehydrogenase, phosphorus, potassium, sodium, total bilirubin, total cholesterol, total protein, uric acid. Includes also creatinine, calculated eGFR and BUN for time points that do not include a full chemistry panel.

**Hematology**      complete blood count with differential, hematocrit, hemoglobin, platelet count, red blood cell count, white blood cell count with differential.

Clinical laboratory test values are potentially clinically important (PCI) if they meet either the low or high PCI criteria listed in Table 4. The number and percentage of subjects with post-baseline PCI values will be tabulated by treatment group. The percentages will be calculated relative to the number of subjects with available baseline values and at least 1 post-baseline assessment. The numerator is the total number of subjects with at least 1 post-baseline PCI value. A supportive listing of subjects with post-baseline PCI values will be provided including the subject number, site, baseline, and post-baseline values.

All clinical laboratory data will be listed, including pregnancy.

**Table 4: Criteria for Potentially Clinically Important Laboratory Tests**

Parameter	Lower Limit	Higher Limit
Biochemistry		
Alanine aminotransferase (ALT)	NA	$\geq 3 \times \text{ULN}$
Alkaline phosphatase (ALP)	NA	$\geq 3 \times \text{ULN}$
Aminotransferase (AST)	NA	$\geq 3 \times \text{ULN}$
Blood urea nitrogen (BUN)	NA	$\geq 30 \text{ mg/dL}$
Creatinine	NA	$\geq 250 \text{ umol/L}$
Total bilirubin	NA	$\geq 2 \text{ mg/dL}$
Troponin	NA	NA
Hematology		
White blood cell (WBC)	$\leq 2.8 \times 10^3/\text{mm}^3$	$\geq 16 \times 10^3/\text{mm}^3$
Hemoglobin	8 g/dL	NA
Hematocrit	$\leq 24\%$	NA
platelet count	$\leq 75 \times 10^3/\text{mm}^3$	NA

### 11.3 Vital Signs

Descriptive statistics for vital signs (e.g. systolic and diastolic blood pressure, and pulse) and their changes from baseline at each post-baseline visit will be presented by treatment group. Baseline is defined as the last measurement prior to the first dose of investigational product during the study.

Vital sign values will be considered PCI if they meet the observed value criteria and the change from baseline criteria listed in Table 5. The number and percentage of subjects with PCI post-baseline values will be tabulated by treatment group. The percentages will be calculated relative to the number of subjects with baseline and at least 1 post-baseline assessment. The numerator is the total number of subjects with at least 1 PCI post-baseline vital sign value. A supportive listing of subjects with post-baseline PCI values will be provided including the subject number, site, baseline, and post-baseline PCI values.

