6.2.3 Dosing

Eligible subjects in this study will receive a total of 7 doses of investigational product over a 13-day period: an initial 100 mL IV infusion containing 5000 U CINRYZE or placebo (100 mL 0.9% sodium chloride for infusion) on Day 1, followed by 2500 U of CINRYZE in 100 mL of IV infusion or placebo (100 mL 0.9% sodium chloride for infusion) IV on Days 3, 5, 7, 9, 11, and 13 (Table 4). If DSA reduction therapy occurs on the same day as investigational product dosing, investigational product will be administered after completion of the plasmapheresis, plasma exchange or immune adsorption treatment session and dosing of the sucrose-free IVIg.

Table 4 Investigational Product Dosing Day, Volume and Amount

	Volume	CINRYZE	Placebo
Day 1	100 mL	5000 Units of CINRYZE (50 mL of CINRYZE/ 50 mL of normal saline)	100 mL of normal saline
Day 3, 5, 7, 9, 11, and 13	100 mL	2500 Units of CINRYZE (25 mL of CINRYZE/ 75 mL of normal saline)	100 mL of normal saline

Note: All doses must be brought up to 100 mL

Additionally, if a study subject has resolution of their qualifying episode of acute AMR and, during the first 180 days after the biopsy of the qualifying episode of AMR, has a new episode of AMR as defined in Section 3.1, the subject may be retreated with investigational product per the same randomization assignment per protocol.

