7.2.2.8 Donor-specific Antibody Reduction Treatments and Intravenous Immunoglobulin

To reduce DSA, subjects will be required to receive a minimum of 5 plasmapheresis, plasma exchange, or immune adsorption treatments (the choice of any of these procedure(s) will be based on standard-of-care at each study site) from the time of diagnostic biopsy for qualifying episode of acute AMR through Study Day 13. Each DSA reduction treatment will be followed by no less than 100 mg/kg sucrose-free IVIg. Protocol-mandated plasmapheresis, plasma exchange, or immune adsorption treatments should be completed by Day 13. Additional DSA reduction treatments and sucrose-free IVIg may be administered at the discretion of the investigator as part of standard of care. NOTE: If plasmapheresis, plasma exchange, or immune adsorption treatment occurs on the same day as investigational product dosing, investigational product will be administered after completion of the DSA treatment session and dosing of sucrose-free IVIg. Blood collection for laboratory assessments, other than those specified on [Table 3](#), should be performed prior to the DSA reduction treatments. Investigators will record details of each DSA reduction treatment and each sucrose-free IVIg dose in the CRF.

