7.2.3.4 Vital Signs

Vital signs include blood pressure and pulse. Any deviations from Screening in vital signs that are deemed clinically significant in the opinion of the investigator are to be recorded as an AE. On investigational product dosing days, vital signs should be obtained within 30 minutes prior to investigational product administration and then between 30 minutes and 1 hour after completion of investigational product infusion. Additional vital signs measurements will be performed during the study if clinically indicated.

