8.1.4 Adverse Events of Special Interest

In addition, the following events of special interest, both serious and non-serious, will be closely monitored and reported to Shire PVRM via SAE form throughout the study, regardless of relationship to investigational product:

- Any thrombotic or thromboembolic event: thrombotic or thromboembolic events will be assessed for relatedness to investigational product. Stopping rules related to thrombotic or thromboembolic events are described in Section 4.5.3.
- Any hypersensitivity reaction
- Any new episode of kidney allograft rejection (excluding AMR)
- Kidney allograft failure as defined in Section 7.2.2.5

AESIs reported via SAE form that do not meet the serious criteria definition (Section 8.2.3) should be reported on the SAE form as being non-serious.

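### Vital signs bracket every infusion, but SAP 11.3 plans no same-day post-minus-pre change, so on Days 3–13 and in retreatment infusion effects are mixed with background shifts (minor, cheap to improve)

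*SAP*

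**What the plan says.** Protocol 7.2.3.4 and footnote d of Table 1 (Schedule of Assessments) require dosing-day vital signs "within 30 minutes prior to investigational product administration and then between 30 minutes and 1 hour after completion of investigational product infusion". Protocol 6.2.3 gives the number of infusions: "Eligible subjects in this study will receive a total of 7 doses of investigational product over a 13-day period". A full course therefore yields seven bracketing pairs.

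SAP 11.3 plans descriptive statistics for the values and states that "their changes from baseline at each post-baseline visit will be presented by treatment group". The reference is fixed: "Baseline is defined as the last measurement prior to the first dose of investigational product during the study". It is not reset for a later infusion or a retreatment course. For flags, "Vital sign values will be considered PCI if they meet the observed value criteria and the change from baseline criteria listed in Table 5". For low systolic pressure, Table 5 requires an observed value of 90 mmHg or less together with a fall of 20 mmHg or more. SAP 18.3 lets every post-baseline assessment enter the overall PCI determination.

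On days with antibody-reduction treatment, Protocol 7.2.2.8 sets the order: "investigational product will be administered after completion of the DSA treatment session and dosing of sucrose-free IVIg". Protocol 8.1.4 lists "Any hypersensitivity reaction" among the events of special interest.

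The outputs in SAP section 20 are Table 14.3.5.1 (actual values and change from baseline), Table 14.3.5.2 (PCI vital signs) and Listing 16.2.8.2.1. All three are kept for the abbreviated report.

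**The concern.** The schedule supplies a before-and-after pair for each infusion, yet no planned statistic subtracts one from the other. Protocol 9.10 does plan a pre- to post-infusion change for C3a and C5a, so the idea is already in the study.

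From Day 3 onward, the difference between a post-infusion reading and the first-dose baseline also contains changes over the intervening days and the effect of any plasmapheresis and IVIg earlier that day. In retreatment the baseline can be months old, because Protocol 3.1 allows retreatment for recurrences biopsied up to 180 days after the qualifying biopsy. A pre-infusion reading cannot show a reaction to an infusion not yet given, but it can trigger a PCI flag.

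At stake is how readable the by-arm vital-sign tables are. Protocol 8.2.1 notes that earlier experience at this dose in this population is 9 subjects, with no expected reactions yet defined. No test, alpha level, endpoint or decision rule depends on these tables.

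**Working it through.** The plan states no figure on this point, so there is none to reproduce. The check sets the data collected against the statistic planned, then sizes the difference under stated assumptions.

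**Which readings are affected**
- Seven infusions with two readings each give 14 readings. The Day 1 pre-infusion reading is normally the baseline, which leaves 13: 7 post-infusion and 6 pre-infusion.
- Day 1 (1 of 7 infusions): post-infusion minus baseline equals post minus same-day pre.
- Days 3–13 (6 of 7) and every retreatment infusion: the two differ by the shift between the baseline and that day's pre-infusion reading.

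**A single hypothetical case under Table 5 (systolic, mmHg).** Baseline 115, pre-infusion 88, post-infusion 88. The change across the infusion is 0. The change from baseline is 88 − 115 = −27 and the value is below 90, so the subject is flagged, at the pre-infusion reading already.

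**Precision.** Assumptions, none from the documents: systolic SD 18 mmHg; same-day correlation 0.8 (range 0.7–0.9); cross-day correlation 0.5 (range 0.3–0.6). The SD of a change is SD × √(2(1 − r)).
- From the first-dose baseline: 18 × √(2 × 0.5) = 18.0 mmHg.
- Within the day: 18 × √(2 × 0.2) = 11.4 mmHg.
- SD ratio 18.0/11.4 = 1.58; variance ratio 0.5/0.2 = 2.5.
- Range of the SD ratio: √(0.4/0.3) = 1.15 to √(0.7/0.1) = 2.65.

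**False flags under the full low-systolic rule.** Simulation of 200,000 subjects over one course with no drug effect. Each reading is the mean plus 18 times the sum of normal subject, day and reading components with variances 0.5, 0.3 and 0.2. The SAP rule applies both Table 5 limits to the 13 post-baseline readings. The same-day rule applies both limits to the 7 post-infusion readings, with that day's pre-infusion reading as reference.

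| Assumed mean systolic | SAP rule | Same-day rule |
|---|---|---|
| 125 mmHg | 10.2% | 2.5% |
| 135 mmHg | 3.4% | 0.8% |
| 140 mmHg | 1.8% | 0.4% |

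Among subjects flagged by the SAP rule, about a third at mean 125, rising to about 40% at mean 140, are flagged on pre-infusion readings alone. The gap depends on the correlations. With the same model at mean 135 it is 2.8% v 1.4% for 0.7/0.6 and 4.1% v 0.1% for 0.9/0.3.

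**With a drug effect**
- A fall of 8 mmHg after each infusion (mean 130, correlations 0.8/0.5): the SAP rule goes from 6.2% to 13.2%, the same-day rule from 1.5% to 8.1%. The absolute rises are alike (7.0 and 6.6 points). The ratios are not (13.2/6.2 = 2.1; 8.1/1.5 = 5.4).
- A fall of 15 mmHg (mean 135): 17.5% v 14.8% at 0.8/0.5, 15.5% v 15.3% at 0.7/0.6, and 20.8% v 12.6% at 0.9/0.3. The SAP rule flags at least as many subjects in each case.

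**The case against.** The case for leaving the plan alone is substantial, and most of it stands.

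- A reader might infer that only change from baseline is analysed. It is not. Actual values are tabulated, absolute limits apply and every reading is listed.
- A reader might infer that the Day 1 post-infusion reading drops out because Day 1 is the baseline visit. The documents do not support this. The reading is post-baseline by definition and SAP 18.3 admits it to the PCI determination. The table shells are in a separate document not available here, so the row layout is unknown.
- A reader might infer that real reactions would go unflagged. Single cases exist: baseline 105, pre-infusion 135, post-infusion 88 is a 47 mmHg fall, but only −17 from baseline, so it is not flagged. In aggregate this does not show. With the 15 mmHg fall above, the SAP rule flags as many subjects or more.
- A reader might take the pairing as designed to detect acute reactions. That is a fair inference from the timing, but the documents do not state it. Hypersensitivity reactions are reported as events of special interest, and clinically significant vital-sign deviations are recorded as adverse events. The latter route rests on investigator judgement relative to Screening, which is also a remote reference.
- Drift and plasmapheresis affect both randomised arms, so they add noise rather than bias.

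What remains is that, for 6 of 7 first-course infusions and all retreatment infusions, no planned statistic isolates the change across the infusion. Splitting pre- and post-infusion rows in the shells would leave the change column and the PCI rule on the first-dose baseline.

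**Conclusion.** The point holds as a minor gap in a descriptive safety analysis, confined to Days 3–13 and retreatment. The same-day change is the better measure of an infusion effect, and its data are already collected. The gain is precision and specificity: at the central assumptions the variance of the change falls to 40% (0.2/0.5), and false low-systolic flags fall roughly four-fold (10.2/2.5 = 4.1 at mean 125; 1.8/0.4 = 4.5 at mean 140). These sizes rest on assumed means, SD and correlations and on a normal model. They cover low systolic pressure in one course only. The finding that no same-day change is planned needs none of these assumptions. Efficacy conclusions, type I error and power are untouched.

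**What to change.** - **SAP 11.3 and Table 14.3.5.1:** tabulate pre- and post-infusion readings separately on each dosing day, naming the Day 1 post-infusion reading explicitly. Add post-infusion minus same-day pre-infusion change by arm and treatment period.
- **Table 14.3.5.2:** beside the existing row, add one that applies the existing Table 5 limits to post-infusion values, with the same-day pre-infusion value as the reference for change.
- **Keep** the existing change-from-baseline summaries.

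The cost is programming a few rows and a slightly longer descriptive safety table. No new measurement is needed, and neither the efficacy analyses nor patient management changes.

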**Table 5: Criteria for Potentially Clinically Important Vital Signs**

Vital Sign Parameter	Flag	Criteria Values	
		Observed Value	Change from Baseline
Systolic blood pressure (mmHg)	High	≥180	Increase of ≥20
	Low	≤90	Decrease of ≥20
Diastolic blood pressure (mmHg)	High	≥105	Increase of ≥15
	Low	≤65	Decrease of ≥15
Pulse rate (beats per minute)	High	≥120	Increase of ≥15
	Low	≤50	Decrease of ≥15

## 11.4      **Electrocardiogram (ECG)**

All ECG data (e.g. heart rate, RR, PR interval, QRS interval, QT interval, and QTc interval) including ECG abnormalities as reported by the investigators will be provided in the listings. QTc interval will be calculated using both Bazett ( $QTcB=QT/(RR)^{1/2}$ ) and Fridericia ( $QTcF=QT/(RR)^{1/3}$ ) corrections.

## 11.5      **Physical Examinations and lower extremity exam**

Abnormalities identified during the Physical Examination done at the Screening Visit will be documented in the subject's source documents and on the medical history CRF. If the abnormality is clearly caused by an event that occurred after the subject signed informed consent and before the Physical Examination of the Screening Visit, the event will be captured as an AE. Changes after the Physical Examination of the Screening Visit will be captured as AEs on the AE CRF page, as deemed by the investigator.

Additionally, a lower extremity exam will be performed at specified time points (Table 1) and will include a determination of presence or absence of unilateral calf tenderness or leg swelling that may be new since the previous examination. If a DVT is suspected, a diagnostic study will be performed.

Lower extremity exam results will be provided in the listings.

## 11.6      **Immunogenicity (Anti-C1 INH)**

The positive and negative counts of Immunogenicity (Anti-C1 INH) samples will be summarized by visit and treatment for the Safety Analysis Set. Baseline is defined as the last measurement before first dose of investigational product. All immunogenicity data will be listed.

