^c In addition to Central laboratory testing, the local laboratory must obtain BUN, and creatinine values and calculate eGFR values for documentation in CRFs for each of the time points indicated as well as pre-AMR and resolution of AMR for all AMR episodes. Subjects who discontinue before 6 months should complete the Early Discontinuation Visit Between Day 13 & Month 6.

Table 2 Schedule of Assessments (Month 3 through Month 48 [End of Study])^a

Study Procedure	Post-Treatment Evaluations									
	Month 3 (±21 days) ^b	Month 6 (±21 days) ^b	Month 12 (±21 days) ^b	Month 18 (±28 days) ^b	Month 24 (±28 days) ^b	Month 30 (±28 days) ^b	Month 36 (±28 days) ^b	Month 42 (±28 days) ^b	Early Discontinuation Visit Between Day 13 & Month 6	EOS/Month 48 or at patient discontinuation if after Month 6 (±28 days) ^b

^d In the event of discontinuation of a fully-dosed subject prior to the Month 6 Visit, every attempt will be made to obtain a biopsy at discontinuation to send to the independent, blinded pathology EAC for determination of TG. The required slides and images for the Screening, Month 6, early discontinuation before Month 6 (if applicable), and any other unscheduled standard of care biopsies, must be submitted to the Sponsor's designee within 30 days after the biopsy procedure, for subsequent submission to the EAC for review.

^e Subjects where anti-C1 INH antibodies are detected will be followed to measure titers. At Months 12, 18, 24, 36, and 48 the test will be performed ONLY if anti-C1 INH antibodies are detected at the previous time point. At Month 3 and Month 6 the test will be performed in each patient.

^f DSA antibody analysis will be performed by the central laboratory and will not be reported back to the investigator. Additional DSA testing at these and other time points may be performed by the local laboratory for all clinical assessments as part of standard of care. Additional serum may be collected for the central laboratory for future antibody and titer testing.

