Blood samples will be collected at screening (pre-dose sample should always be collected at screening), on Day 25, and at Months 3 and 6 for determination of anti-C1 INH antibodies. If sucrose-free IVIg is administered at the screening visit, a sample for anti-C1 INH will be collected before (pre-dose sample) and after sucrose-free IVIg administration (post-dose sample). Subjects with anti-C1 INH antibodies will be followed at the time points specified in [Table 2](#), to measure titers. For Months 12, 18, 24, 36, and 48 the test will be performed ONLY if anti-C1 INH antibodies are detected at the previous time point. For Months 3 and 6 the test will be performed for each subject. See [Table 2](#).

Pharmacokinetic/Pharmacodynamic Assessments

See section [7.2.4.1](#)

Urinalysis

A urine sample will be collected at the visits specified on [Tables 1](#) and [2](#) for the assessment of proteinuria, to include spot urine protein, urine creatinine, and urine protein to creatinine ratio.

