**Table 2 Schedule of Assessments (Month 3 through Month 48 [End of Study])a**

Study Procedure	Post-Treatment Evaluations								
	Month 3 (±21 days) b	Month 6 (±21 days) b	Month 12 (±21 days) b	Month 18 (±28 days) b	Month 24 (±28 days) b	Month 30 (±28 days) b	Month 36 (±28 days) b	Month 42 (±28 days) b	Early Discontinuation Visit Between Day 13 & Month 6

b Visit dates for each visit from Month 3 through EOS will reference back to Day 1 of study entry and will be based on calendar months. Visit windows for each visit in [Table 2](#) will be ±21 days for Months 3, 6, and 12. Visit windows will be ±28 days for Months 18, 24, 30, 36, 42, 48, Early Discontinuation, and End of Study (EOS).

c In addition to Central laboratory testing, the local laboratory must obtain BUN, and creatinine values and calculate eGFR values for documentation in CRFs for each of the time points indicated as well as pre-AMR and resolution of AMR for all AMR episodes. Subjects who discontinue before 6 months should complete the Early Discontinuation Visit Between Day 13 & Month 6.

d In the event of discontinuation of a fully-dosed subject prior to the Month 6 Visit, every attempt will be made to obtain a biopsy at discontinuation to send to the independent, blinded pathology EAC for determination of TG. The required slides and images for the Screening, Month 6, early discontinuation before Month 6 (if applicable), and any other unscheduled standard of care biopsies, must be submitted to the Sponsor's designee within 30 days after the biopsy procedure, for subsequent submission to the EAC for review.

e Subjects where anti-C1 INH antibodies are detected will be followed to measure titers. At Months 12, 18, 24, 36, and 48 the test will be performed ONLY if anti-C1 INH antibodies are detected at the previous time point. At Month 3 and Month 6 the test will be performed in each patient.

f DSA antibody analysis will be performed by the central laboratory and will not be reported back to the investigator. Additional DSA testing at these and other time points may be performed by the local laboratory for all clinical assessments as part of standard of care. Additional serum may be collected for the central laboratory for future antibody and titer testing.

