## 11. SAFETY ANALYSES

The safety analysis will be performed using the Safety Analysis Set, unless specified otherwise. Safety variables include TEAEs, clinical laboratory variables, vital signs, lower extremity exam, and C1 INH antibody variables. For each safety variable, the last value collected prior to the first dose of investigational product during the study will be used as baseline for all analyses of that safety variable.

Summary statistics and changes from baseline to post-baseline for clinical laboratory testing, vital signs, diabetes status, and lower extremity exam by treatment group will be presented. For the clinical laboratory testing results, only the scheduled central lab data will be included in the summary tables. All unscheduled or local lab data will only be provided in the listing.

Number, severity, and causality of AEs will be summarized by treatment group.

Results of C1 INH antibody testing will be reported for individual subjects and summarized as appropriate.

A Final on-Treatment Assessment (FoTA) is defined as the last valid assessment obtained up to 30 days after the last dose of the investigational product during the study.

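### SAP 11.6 counts anti-C1 INH samples by visit and arm but gives no subject-level treatment-emergent antibody incidence, and its rows from Month 12 show persistence, not prevalence

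*SAP*

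**What the plan says.** SAP 11.6 has three instructions. The summary is: "The positive and negative counts of Immunogenicity (Anti-C1 INH) samples will be summarized by visit and treatment for the Safety Analysis Set". The baseline rule is: "Baseline is defined as the last measurement before first dose of investigational product". The third is: "All immunogenicity data will be listed". The introduction to SAP section 11 adds: "Results of C1 INH antibody testing will be reported for individual subjects and summarized as appropriate". No text in 11.6 defines a shift, a seroconversion, an ever-positive subject or a treatment-emergent category.

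The testing schedule has two parts.
- **Through Month 6, everyone is tested.** Protocol 7.2.3.5.1 schedules samples at screening, "on Day 25, and at Months 3 and 6 for determination of anti-C1 INH antibodies". SAP Table 2, footnote e, confirms: "At Month 3 and Month 6 the test will be performed in each patient".
- **From Month 12, testing depends on the last result.** For Months 12, 18, 24, 36 and 48, protocol Table 2 footnote e (repeated in the SAP) says "the test will be performed ONLY if anti-C1 INH antibodies are detected at the previous time point".

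Two rules can give one subject more than one sample under a visit label. If sucrose-free IVIg is given at the screening visit, protocol 7.2.3.5.1 says "a sample for anti-C1 INH will be collected before (pre-dose sample) and after sucrose-free IVIg administration (post-dose sample". A retreated subject also goes through Table 1 again from Day 1 (Table 1, footnote i), and that schedule includes the Day 25 antibody sample.

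SAP section 20 keeps Table 14.3.6.1 (immunogenicity by visit and arm) and Listing 16.2.8.5 for the abbreviated study report.

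**The concern.** Antibodies to C1 INH are a named safety endpoint (protocol 9.9). The usual safety question is how many subjects without antibodies before dosing developed them afterwards, and whether that differs by arm. Counts of positive and negative samples at each visit do not answer it. They do not link a subject's later result to the baseline result, and they do not show whether positives at successive visits are the same people.

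The rows also differ in kind. Those to Month 6 describe the whole arm; those from Month 12 describe a group selected for having been positive. Set out in one table without a label, the later rows invite a reader to see a prevalence that they do not measure.

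**Working it through.** The documents give no expected antibody rate, so there is no planned figure to reproduce. Every antibody rate below is an assumption. The arm size of 56 is the planned one (SAP 2.5).

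**1. What visit totals say about seroconversion.** Let N subjects all be tested, with P0 positive at baseline and P1 positive at a later visit. The number S who went from negative to positive satisfies max(0, P1 − P0) ≤ S ≤ min(P1, N − P0). With N = 56:
- P0 = 3, P1 = 3: S lies between 0 and 3, that is 0% to 3/53 = 5.7% of baseline-negative subjects.
- P0 = 3, P1 = 8: S lies between 5 and 8.
- P0 = 0, P1 = 6: S is exactly 6.

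The totals settle the matter only when nobody is positive at baseline, or in similarly extreme cases.

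**2. Ever positive across three visits.** If 3 of 56 are positive at each of Day 25, Month 3 and Month 6, the number ever positive is between 3 (the same people) and 9 (all different): 3/56 = 5.4% to 9/56 = 16.1%.

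**3. Rows from Month 12.** Suppose 3 of 56 (5.4%) are positive at Month 6. Only those 3 are tested at Month 12. If 2 remain positive, the row shows 2/3 = 67%, while the share of the arm known to be positive is 2/56 = 3.6%. Over a range of Month 6 positivity from 2% to 20%, about 1 to 11 of 56 are tested (56 × 0.02 = 1.1; 56 × 0.20 = 11.2). With 50% to 80% persistence, the row reads 50% to 80%, against 0.02 × 0.5 = 1% to 0.20 × 0.8 = 16% of the arm. The row percentage simply is the assumed persistence. If all 3 clear, it reads 0 of 3.

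**4. Paired screening samples, if samples are the unit.** Let a share s of subjects give two samples, b be the positivity before IVIg, and r the proportion of otherwise negative post-IVIg samples that turn positive. The sample percentage is [b + s(b + (1 − b)r)] / (1 + s). With b = 3% and s from 25% to 100%, 56 subjects give 70 to 112 samples. If r = 0 the percentage stays at 3%. If r = 10% it is 4.9% at s = 25% and 7.9% at s = 100%. This affects the screening row only.

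**5. What the fully tested rows can show.** No test between arms is planned, but power indicates how visible an excess would be. By the normal approximation, power = Φ((|p1 − p2| − 1.96·se0)/se1), with se0 from the pooled proportion and se1 unpooled. For 2% against 20% at 56 per arm: se0 = √(0.11 × 0.89 × 2/56) = 0.0591, se1 = √((0.0196 + 0.16)/56) = 0.0566, so power = Φ((0.18 − 0.1159)/0.0566) = 87%. For 2% against 10% and 30% it is 43% and 99%. SAP 17 reports that the trial was discontinued after the first interim analysis, planned at 30 Month 6 completers. The final arm sizes are not given. At an assumed 15, 25 or 35 per arm, power for 2% against 20% is about 34%, 53% or 68%; the approximation is rough at these sizes.

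**The case against.** A reader might infer that the table cannot show whether CINRYZE induces antibodies. The documents do not support that. The Day 25, Month 3 and Month 6 rows are unselected, placebo-controlled and split by arm, and step 5 shows that a large excess would be visible at the planned size. Nor is the table the only planned output: results are listed by subject, Listing 16.2.8.5 is retained, and SAP section 11 allows further summary where appropriate. Seroconversion can be derived from the listing. These points stand. They show that the information exists, not that the plan specifies the summary.

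It is also tempting to say that the positive share rises after Month 6 purely because of the testing rule. It need not rise, since everyone still followed may clear.

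A third inference is that the pre-IVIg screening sample should be the baseline. Table 1, footnote m, allows IVIg as standard of care before study entry, so a single screening sample may already follow IVIg and a clean pre-IVIg sample may not exist. If IVIg itself turned a sample positive, that baseline could label the subject treatment-emergent before any study drug. The SAP's last-before-dosing rule is deterministic and matches its baseline for other safety variables.

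Two further defences stand in part. SAP 18.1 summarises categorical variables by number of subjects, and the table shells are a separate document, so double counting is possible rather than certain. The analysis is also descriptive with no alpha attached, and the selected denominator can be recovered by adding positives and negatives.

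**Conclusion.** The point holds as a cheap improvement to a retained safety table. SAP 11.6 defines a baseline it does not use and gives no treatment-emergent incidence by arm. Its rows from Month 12 are conditional on earlier positivity and are not labelled so. It does not say how paired screening samples or a second Day 25 sample enter the counts.

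The size depends on antibody rates that the documents do not give. With 3 of 56 positive at baseline and at Month 6, seroconversion is undetermined between 0 and 3 subjects. With 3 of 56 at each of three visits, ever-positive lies between 5.4% and 16.1%. A Month 12 row of 67% can stand beside 3.6% of the arm known to be positive. These figures assume full attendance and the planned arm size. Because by-timepoint outputs stop at study termination (SAP 17), the late rows may be sparse, and in smaller arms the fully tested rows reveal less on their own.

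**What to change.** In SAP 11.6 and Table 14.3.6.1:
1. Count each subject once per visit. Keep the existing baseline rule, and show the other sample of any screening pair, and samples from a retreatment period, separately.
2. By arm, report the number and percentage of baseline-negative subjects with a post-dose sample who are positive at any of Day 25, Month 3 or Month 6. Show baseline-positive subjects separately.
3. From Month 12, present results as persistence among subjects positive at the previous test, with the number tested as denominator.
4. Keep the sample-level results in Listing 16.2.8.5.

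The cost is SAP wording, one derived variable and one extra table block. All of it uses data already scheduled for collection, and no visit, sample or treatment changes.
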